Pilot Testing a Home-Based Rehabilitation Intervention Designed to Improve Outcomes of Frail Veterans  
Following Cardiothoracic Surgery

NCT03299101

7/24/2020

1.0 \* Study Name:

Home-based Rehabilitation Before Cardiothoracic Surgery (Pilot)

2.0 \* Brief Description (using layman's terms) - 500 words or less:

Frail Veterans are at increased risk for poor surgical outcomes, and as the Veteran population grows older and more frail, there is a critical need to identify effective strategies for reducing surgical risks for these patients. Prior research shows that inter-disciplinary rehabilitation strategies deployed after surgery enhance recovery and improve outcomes by building strength and improving nutrition. We believe that similar improvements may be obtained by using similar interventions before surgery to "prehabilitate" patients' capacity to tolerate the stress of surgery. The proposed research will examine the feasibility of a novel, multifaceted, home-based prehabilitation intervention designed to improve functional capacity and postoperative outcomes for frail Veterans anticipating cardiothoracic surgery. Findings from the study will inform the design of a larger randomized controlled trial of the prehabilitation intervention. If proven effective, prehabilitation could benefit as many as 42,000 frail Veterans who are scheduled for major elective surgery each year.

\* Abstract. Please provide a brief description of the study.

Background: Frail Veterans are at increased risk for poor surgical outcomes. Although surgical techniques have advanced to a level where surgery on very old adults is feasible, if a patient is also frail, the stress of surgery may overwhelm their adaptive capacities, placing them at increased risk of mortality, morbidity, and institutionalization even if surgery is technically successful. Frailty is a clinical syndrome that is commonly characterized by muscle atrophy, diminished strength and speed, decreased physical activity, and exhaustion. It is independent of any specific disease, but it increases with age and worsens disease prognoses by diminishing capacity to tolerate stressors. Thus, while surgery is often indicated for older patients, frail candidates are less likely than robust counterparts to tolerate the procedure and/or recover functional capacity. In fact, recent VA data demonstrate that frailty is a more powerful predictor of increased perioperative mortality, morbidity, length of stay, and cost than predictions based on age or comorbidity alone. As the Veteran and US populations grow older, frailty will increase, making it critically important to identify effective strategies for improving the surgical recovery and outcomes of frail patients.

"Prehabilitation" has the potential to improve surgical outcomes among the frail. Prior research demonstrates that inter-disciplinary rehabilitation strategies deployed after surgery enhance recovery and improve outcomes by building strength and improving nutrition. Based on this success, there is growing interest in "prehabilitation", which is a similar intervention deployed before surgery. By modifying physiological and environmental risks, prehabilitation aims to augment patients' capacity to compensate for the stress of surgery itself and the convalescent period thereafter. Frail patients may benefit disproportionately from prehabilitation because they have diminished capacity to endure the procedure and/or recovery. Preliminary evidence suggests that preoperative exercise interventions improve surgical outcomes. However, prehabilitation has not yet been studied in either Veteran or specifically frail populations, and no prior studies used home-based prehabilitation strategies to safely minimize travel-related barriers to participation.

Objectives: We will examine the feasibility of a novel, multifaceted, home-based prehabilitation intervention designed to improve functional capacity and postoperative outcomes for frail Veterans anticipating cardiothoracic surgery. Specific aims are to:

- (1) Estimate rates of recruitment, retention, and adherence to the intervention; and evaluate participation barriers.
- (2) Measure changes over time in frailty, physical function, pulmonary function, nutrition, and health-related quality of life at baseline, the day of surgery, and 30 and 90 days after surgery.
- (3) Explore changes in postoperative mortality, major complications, length of hospital stay, and level of independent living using case-matched historical controls.

**Methods:** This single-arm pilot study will enroll a consecutive cohort of up to 50 Veterans identified as frail using a standardized frailty assessment and scheduled for major cardiothoracic surgery at the VA Pittsburgh Healthcare System. The 4 week long prehabilitation regimen will include: (a) aerobic conditioning, (b) strength and coordination training, (c) respiratory muscle training, and (d) nutritional coaching and supplementation. Pre- and post-prehabilitation assessments will include: (a) frailty; (b) physical function; (c) pulmonary function; (d) nutrition; and (e) health-related quality of life. Postoperative outcomes will include length of stay, mortality

#### Research Study Methods

##### View: 4 Research study methods

\* Research Procedures/Interventions:

#### Research Procedures/Interventions:

**C.1. Overview.** In this single-arm pilot study, we will enroll a consecutive cohort of up to 50 Veterans identified as frail using a standardized frailty assessment and scheduled for major cardiothoracic surgery at the VA Pittsburgh Healthcare System. The 3-6 week long prehabilitation regimen will include: (a) aerobic conditioning, (b) strength and coordination training, (c) respiratory muscle training, and (d) nutritional coaching and supplementation. Pre- and post-prehabilitation assessments will include: (a) frailty; (b) physical function; (c) pulmonary function; (d) nutrition; and (e) health-related quality of life. Using physical performance tests, biomarkers, chart review, survey instruments, and patient logs, we will assess the feasibility of the recruitment, randomization, retention and assessment procedures, compensating patients for their time. Prehabilitation will not last more than 4 weeks for CABG patients. However, for non-cardiac thoracic patients, prehabilitation may be extended out to 6 weeks if the surgeon and patient so choose.

**C.2. Eligibility criteria.** We will recruit frail patients (i.e., RAI $\geq$ 16 and Physician /Provider request for patient with RAI<16) scheduled for a CABG or Valve Surgery. Major non-cardiac thoracic surgery is defined according to VA Surgical Quality Improvement Program (VASQIP) criteria that include cases requiring general, epidural, or spinal anesthesia. It includes 193 unique CPT codes ranked by complexity (26 standard, 146 intermediate, and 21 complex) and excludes 58 low risk “minor” surgical procedures with limited morbidity (e.g., bronchoscopy, percutaneous lung biopsy). From these major surgeries, we will include those procedures that deliberately violate the visceral or parietal pleura with something larger than an 18 gauge needle. For example, we will include lung and esophagus resections of all kinds, but exclude thoracentesis. Exclusion criteria are designed to ensure participant safety in prehabilitation exercises (e.g., low-risk, stable cardiac disease without significant symptoms, arrhythmias, hemodynamic instability or critical coronary lesions). Based on historical data, we expect 2/3rds of eligible

patients to exhibit mild frailty (RAI 16-25) with essentially intact independence and capacity for prehabilitation. Higher degrees of frailty may impose barriers to full participation, but characterizing those limitations is an important component of this pilot. We will stratify enrollment to ensure approximately equal enrollment of cardiac and non-cardiac thoracic patients.

**C.3. Prehabilitation procedures.** Prehabilitation will last 3-6 weeks—a time frame that does not delay surgery, corresponds to the typical lag for surgical scheduling, and strikes a pragmatic balance between improving physiologic reserve without unduly delaying definitive surgical therapy. Although the training intervention is only 3-6 weeks, studies repeatedly demonstrate neuromuscular strengthening, diminished inflammation, and respiratory improvements within this time. Further, the program also fosters continuity between preoperative training and traditional postoperative rehabilitation, facilitating rapid mobilization and progressive exercise after surgery. Strategies like this enhance functional recovery and reduce the risks of subsequent episodes of disability (e.g., readmission or loss of independence). If clinical contexts such as neoadjuvant chemotherapy or worsening angina require shorter (or permit longer) durations of training, we will examine these events in order to inform the optimal duration of prehabilitation for a larger clinical trial.

**(a) Safety.** Prehabilitation will begin in a telemetry-monitored, hospital-based setting to train patients in the home-based exercises and establish safe targets of exertion. If and as safety is established, exercise will shift to the home with weekly telephone/ VA Video Connect contact to ensure safety and reinforce technique. Remote telephone and VA Video Connect monitoring will be enhanced by the relationships, familiarity, and trust established during the hospital-based sessions. Although safety concerns will require some patients to complete all exercise in monitored, hospital-based settings, we anticipate that many patients will safely transition to home-based exercise after 1-4 hospital-based sessions. Study staff will initiate withdrawal procedures for patients who demonstrate insufficient cognitive or physical capacity to safely carry out the prescribed activities.

**(b) Hospital-based training.** Twice weekly 1-hour hospital sessions will be closely monitored and continue until participants demonstrate: (a) mastery of prehabilitation techniques; and (b) compliance with safe targets of exertion that do not induce cardiac symptoms. All patients will complete at least 1 sessions with telemetry to rule-out significant arrhythmia, but they will continue as long as needed to ensure that exercise can safely shift to the home. *Aerobic training* will focus on seated pedaling. Leg pedaling is preferred, but in cases of lower extremity disability, upper extremity exercise will be implemented. After a 3-5 minute warm-up at a low intensity of an 7-9 on the Borg Rating of Perceived Exertion (RPE) scale, patients will be coached to reach 30 minutes of continuous (through bouts of 10 minutes or more to work up to the 30minutes), moderate exertion (RPE 11-13). If this exertion induces cardiac symptoms, the target will be adjusted down until a safe level is established. *Strength training* will use body weight and resistance bands (TheraBand™) at RPE 11-13 to focus on a spectrum of antagonist muscles to support the core abdominal and thoracic muscles impacted by surgery. *Coordination training* will involve exercises designed to strengthen the proper form of transitional movements required after surgery such as lying-to-side-lying, side lying-to-sitting, seated scooting, and sitting-to-standing. *Respiratory muscle training (RMT)* requires that subjects inspire and exhale through a mouthpiece at a comfortable rate using diaphragmatic breathing techniques while wearing a nose clip. The RMT device prohibits subjects from inhaling or exhaling until specific negative or positive pressures are achieved. Thresholds devices will be used and set at 40% of each patient's maximal inspiratory pressure (MIP) performed on the Pro2 device. Training will involve 5-20 breaths depending on patients capacity on the threshold device with resistance increased weekly based on RPE with a goal of moderate exertion (RPE 11-12) on both inhalation and exhalation.

**(c) Home-based Training.** Home-based training will increase gradually to reach the goal duration of 60 minutes allocated between strength training 3 days/week and aerobic, RMT and coordination training 5 days/week. Each session will begin with warm up before focused aerobic (pedal exerciser), strength, coordination, and RMT training, followed by cool down and stretching that matches the routines established during hospital-based training. Each patient will be given a portable, folding pedal exerciser that can be placed on the floor for leg pedaling or on a table for arm pedaling. Based on methods that successfully transition cardiac rehabilitation to the home, exercise physiologists will use weekly, remote, telephone-based/ VA Video Connect calls to maintain relationship, answer questions, adjust goals and coach patients regarding their personally tailored prehabilitation regimens. Patients will record details of each training session in log books, and they may return to the hospital biweekly to assess progress in physical performance, or their biweekly session may be completed via VA Video Connect, at which time exercise physiologists will (a) adjust training goals and exercises, (b) remediate technique as needed; and (c) assess the safety of continued home exercise. Family members or other caregivers can assist patients in completing the log books if needed. Training regimens such as these have been shown to be both safe and effective among the frail elderly.

**(d) Nutritional Counseling.** Standard or care consults with the VAPHS Nutrition Services will coincide with the initial IMPACT clinic visit. Staff nutritionists will administer the Subjective Global Assessment (SGA) of nutrition to identify nutritional needs and classify the patient as either normal or mildly, moderately or severely malnourished. All patients will receive best practice nutritional counseling focused on lean, high protein foods in preparation for surgery. Cardiac rehabilitation personnel/research staff will be trained to assess and reinforce progress on these dietary practices. In addition, standard of care nutritional supplementation will be prescribed to malnourished patients, including Impact® Advanced Recovery, an immunomodulating formula shown to improve outcomes after major surgery. Supplements will be delivered to patient's homes. Patients will also record their meals and supplements in log books, and cardiac rehab personnel/research staff will be trained to monitor and encourage consumption of the supplements as prescribed during the hospital-based coaching sessions. Family members or other caregivers can assist patients in completing the log books if needed.

**(e) Occupational and Physical Therapy (OT/PT).** We will arrange for a standard OT/PT consult to coincide with either the initial IMPACT clinic visit or the first scheduled visit to the Cardiac Rehabilitation facility. Staff therapists will perform routine, standardized assessments of the patient's home, environment and mobility, prescribing and supplying indicated durable medical equipment to aid mobility, exercise, and safe transition to independent living at home after the proposed surgery. As per their usual protocol, the PT/OT consult will consult with the Social Work services to adequately assess the home environment and supports in anticipation of postoperative discharge planning.

**C.4. Assessment Schedule (Table1).** As shown in Table 1, research staff will collect baseline data, including demographics, living location, physical performance, and nutrition, at the time of recruitment. Assessments will continue every 2 weeks up to and including the day of surgery, and then postoperatively at 30 and 90 days. Even among the robust, physical performance deteriorates immediately after surgery, but returns to baseline by 90 days. Among the frail, the deterioration may endure, increasing the severity of frailty. Physical Performance Tests will be administered by exercise physiologists in the VAPHS Rehabilitation facility, located near the IMPACT clinic, and thus convenient for patients. Nutrition Assessments include serum prealbumin and c-reactive protein collected each time the participation is onsite for an assessment by a hospital phlebotomists, and the 7-point SGA administered by hospital nutritionists at baseline and again on the day of surgery. Patient Logs will assess patient adherence with the prehabilitation regimen and document progress. Family members or

other caregivers can assist patients in completing the log books if needed. Survey Instruments will be administered either face to face, by telephone/ VA Video Connect, or by mail, depending on patient preference. Responses will be entered directly into REDCap using a project utility distinct from the RAI measurement tool. For patients electing surveys by mail, we will send printed copies of the Redcap forms with a self-addressed, stamped envelope for return. Responses on returned surveys will be keyed into Redcap before storing the paper surveys in locked cabinets. Chart reviews will be completed by research staff to determine details of the surgical procedure, postoperative mortality, length of stay, and major complications. Patient Interviews will be conducted to evaluate barriers to prehabilitation and explore possible solutions. We will also track the time required to complete each measure to inform the design of the subsequent multi-center trial.

Assessments will end after the assessment planned for 90 days after the surgery. Ideally, patients will return to the hospital for this final visit to conduct measures of physical performance and nutrition along with the survey instruments. However, if they are unable to make the visit, we will conduct the surveys over the phone.

Minimizing the Burden of Assessments: Some participants in this study will be concurrently enrolled in a related study of frailty and preoperative palliative care consultation (Pro1840). Some of the outcome assessments planned for Pro 1840 are identical to those planned here. When a participant is enrolled in both studies (Pro1840 and Pro 2192) the study coordinators will work together to ensure that participants do not have to complete identical assessments twice. At any given time point when potentially duplicative assessments could occur, study staff will record the participant's singular response to a duplicative question simultaneously into the case report forms (CRFs) of each separate study. This could be accomplished by having a two separate study staff on the phone or in the room as the patient is interviewed. It could also be accomplished by having a single cross-listed staff member (e.g., listed on the staff form of both studies) administer the assessment and record the responses into the separate CRFs of each study at the same sitting. Additionally, some participants may be concurrently enrolled in a minimal risk study (PI [name] MD; Pro1843) that has similar inclusion criteria. However participation in Pro1843 will not impact the outcomes of this protocol (2192).

To reduce patient burden due to travel once a patient has been determined to be safe to take part in home exercise they will have the option to complete an remote biweekly assessment via VA VideoC onnect. Biweekly Assessments for patients that are unable to make it to the hospital will complete an remote, home-based biweekly assessment while on VA Video Connect with research staff members. VA Video Connect will be used in conjunction with Bluetooth connected peripheral monitors that record and transmit blood pressure, pulse, and oxygen saturation in real time. Single lead cardiac telemetry will also be used once this peripheral is made available (date pending). We will also monitor the patient visually through the video feed to ensure safety. The remote assessment will included the following items form the standard assessment: Five chair rises (standing and siting form a chair 5 times), two 4 meter walks at usual walking speed, assessment of breathing capacity on the threshold trainer (adjusted by RPE scale with goal of RPE 11-13), and if space allows a modified 6 minute walk test.

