**Incidental Findings:** If any of these tests generate an incidental finding of sufficient clinical significance to warrant review by the patient's primary care physician (PCP), we send the test results to the PCP and follow up with an encrypted email. We will also telephone the patient within a week to inform the patient of the finding and the planned PCP follow-up.

**C.8. Data Analysis** will focus on the feasibility of both the intervention and the outcome assessments.

**(a) General approach for quantitative data.** We will first explore the data using descriptive statistics (e.g., means, standard deviations, percentiles, ranges) and graphical techniques (e.g., histograms,

scatter plots) to examine key variables to assess distributional assumptions, the existence of outliers and data sparseness. We will try to minimize the amount of data missing due to dropouts, but will use multiple imputation if indicated.

**(b) Assess the feasibility of a novel prehabilitation intervention by estimating rates of recruitment, retention, and adherence to the intervention, and by evaluating barriers to participation [Aim 1].** We will summarize the total number of eligible patients approached, recruited, and retained through the completion of study procedures 90 days postoperatively, estimating proportions as well as associated confidence intervals (CIs). We will then estimate rates of adherence to the prehabilitation intervention, computing overall and exercise-specific rates (and CIs) for the home and hospital portions of the regimen. Finally, we will qualitatively analyze reported barriers to participation with an eye to identifying potential solutions.

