**(c) Ascertain the feasibility of measuring changes over time in frailty, physical function, pulmonary function, nutrition, and health-related quality of life at baseline, the day of surgery, and 30 and 90 days after surgery [Aim 2].** We will summarize the time required to complete each assessment as well as the completeness of data, estimating completion rates with CIs. Graphical analyses will assess simple changes in frailty, physical performance, pulmonary function, nutrition and quality of life over the study period. Although sample size will limit model fit, we will prepare analyses for the larger trial by developing simple mixed models to explore changes over time (baseline and every other week up to the day of surgery, and then 30 and 90 days after). Separate models for each outcome will assess changes, including a fixed effect for time and a random effect for subject. The type of mixed model will depend on the outcome variable with linear mixed models for continuous variables (e.g., RAI, SPPB, 6MWT, MIP, MEP, etc) and generalized mixed models for ordinal/categorical variables (e.g., SGA, frailty phenotype). We will also explore dose-response relationships based on the actual duration of and adherence to the training regimen.

**(d) Explore changes in postoperative mortality, major complications, length of hospital stay, and level of independent living using case-matched historical controls [Exploratory Aim].** We will match each participant to an historical control using local VASQIP data. VASQIP data include variables sufficient to calculate the RAI as well as details about the patient's procedure, comorbidities, outcomes, and a highly reliable prediction of postoperative 30-day mortality. Each historical control will be chosen from VAPHS VASQIP data from the 2 years prior to the study start and matched to the enrolled participant based on procedure, age, RAI score, and VASQIP predicted mortality. We will summarize separately the total number of deaths and major complications at 30 and 90 days for all patients, estimating proportions with associated CIs for the intervention and historical control groups. We will also compute summary statistics (mean, median, standard deviation, range) for length of hospital stay and return to independent living. We will then attempt to assess if differences exist between the groups with regard to these post-operative measures.

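### Enrolment is balanced between cardiac and non-cardiac thoracic patients, but the Aim 1 recruitment, retention and adherence rates are not planned by that stratum

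*Combined protocol and SAP*

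**What the plan says.** - **Sampling (C.1).** The plan states that "we will enroll a consecutive cohort of up to 50 Veterans identified as frail". The Methods paragraph of the abstract describes the cohort in the same way.
- **Balance (C.2).** "We will stratify enrollment to ensure approximately equal enrollment of cardiac and non-cardiac thoracic patients". No quota, cap or rule for closing a stratum is given, and the natural mix of eligible patients is not stated.
- **Regimen length (C.1).** "Prehabilitation will not last more than 4 weeks for CABG patients", whereas "for non-cardiac thoracic patients, prehabilitation may be extended out to 6 weeks if the surgeon and patient so choose".
- **Aim 1 analysis (C.8(b)).** For recruitment and retention: "We will summarize the total number of eligible patients approached, recruited, and retained through the completion of study procedures 90 days postoperatively", as proportions with confidence intervals. For adherence: "computing overall and exercise-specific rates (and CIs) for the home and hospital portions of the regimen". Surgical group is not named.
- **Aim 2 models (C.8(c)).** These are specified as "including a fixed effect for time and a random effect for subject", so the stratum does not enter there either.

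**The concern.** The cardiac and non-cardiac thoracic split is the one factor that the design controls at enrolment, and the analysis does not use it. The protocol gives grounds for expecting the groups to differ. Their permitted regimen lengths are not the same. C.3 names worsening angina and neoadjuvant chemotherapy as contexts that may alter duration. C.3(b) lowers exertion targets when cardiac symptoms appear.

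Feasibility is the stated focus of the analysis, and the findings are to inform the design of a larger randomised trial. If the programme is workable in one group and not in the other, a single rate will not show it. The pooled rate also depends on the mix that happened to be enrolled, so it cannot be carried to a population with another mix unless the strata behave alike.

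**Working it through.** The maximum of 50 comes without a derivation, so there is no plan figure to reproduce. What can be checked is how a pooled rate behaves.

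**Inputs from the documents:** up to 50 participants (C.1) in approximately equal strata (C.2), hence about 25 + 25 if enrolment is complete.

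**Assumed inputs:** stratum rates of 80% (cardiac) and 60% (thoracic); cardiac share *w* of eligible patients of 0.5, 0.7 or 0.8; 95% intervals (C.8(b) gives no level); retention and adherence taken as proportions of participants. Which group has the higher rate is arbitrary.

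**1. Retention and adherence (denominator: patients enrolled).**
Pooled rate = 0.5 × 0.80 + 0.5 × 0.60 = 70%. Rate in the eligible mix = *w* × 0.80 + (1 − *w*) × 0.60.

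| *w* | Eligible mix | Pooled | Shift |
|---|---|---|---|
| 0.5 | 70% | 70% | 0 |
| 0.7 | 74% | 70% | −4 points |
| 0.8 | 76% | 70% | −6 points |

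In general the shift is (0.5 − *w*) × (difference between strata). For *w* from 0.2 to 0.8 it is at most ±3 points with rates of 80% and 70%, up to ±9 with 90% and 60%, and zero if the strata are alike. The gap hidden by pooling is the full difference, here 20 points.

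**2. Recruitment (denominator: patients approached).**
The formula in step 1 does not apply. To enrol 25 + 25, the number approached is 25/0.8 + 25/0.6 = 31.25 + 41.67 = 72.9, and the pooled rate is 50/72.9 = 68.6%. Against 70%, 74% and 76% for *w* = 0.5, 0.7 and 0.8, the shifts are −1.4, −5.4 and −7.4 points. The stratum with lower uptake needs more approaches, so the pooled rate is off even when eligible patients split 50:50. With 60% and 30%, the number approached is 25/0.6 + 25/0.3 = 125 and the pooled rate is 40%, against 45% at *w* = 0.5 and 54% at *w* = 0.8.

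**3. Sampling error for scale.** Half-width = 1.96 × √(p(1 − p)/n).
- Pooled, p = 0.70, n = 50: 1.96 × √(0.21/50) = 12.7 points.
- One stratum, p = 0.70, n = 25: 1.96 × √(0.21/25) = 18.0 points.
- Recruitment, p = 0.686, n = 72.9: 1.96 × √(0.2154/72.9) = 10.7 points.
- Recruitment, p = 0.40, n = 125: 1.96 × √(0.24/125) = 8.6 points.
- Difference between strata, 80% against 60%, 25 each: 1.96 × √(0.16/25 + 0.24/25) = 24.8 points.

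**The case against.** The strongest reply is that this is a small descriptive pilot and the distortion is hypothetical. The documents give no stratum rates and no natural mix, and the illustrated shifts of 4 to 6 points in retention or adherence lie inside the pooled interval. With 25 per stratum, a 20-point gap has a half-width of 24.8 points, so stratum rates would seldom settle whether feasibility differs. All of that stands, and it limits the weight of the point.

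The reasons to expect a difference are also indirect. The 4-week limit names CABG, while C.2 also admits valve surgery. The thoracic extension is optional, and a longer permitted regimen need not change the proportion who adhere. C.3 will examine events that alter duration, C.8(c) plans a dose-response analysis by actual duration and adherence, and barriers are collected. None of these gives a feasibility rate by surgical group.

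A reader might infer more than the text supports:
- *That an artificial 50:50 mix is imposed.* C.2 says only approximately equal and sets no quota. C.8(e) reports recruitment below expectation, so the balance may never have been reached or may never have constrained enrolment.
- *That C.1 and C.2 contradict each other.* C.1 can be read as consecutive within stratum. It needs clearer wording, but a conflict is not proven.
- *That these rates will set the size of the later trial, or that the natural mix is its target.* The documents say only that the findings will inform its design.

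**Conclusion.** The gap is real and moderate. The plan balances enrolment on a factor and then plans no Aim 1 rate by it, so as written it cannot show whether feasibility differs between the two groups. The main loss is concealment of a difference. The shift in the overall rate is secondary.

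On the assumed 80% and 60%, the shift stays within sampling error for all three kinds of rate. Only a wider gap in recruitment combined with an uneven eligible mix goes beyond it: 60% and 30% at an 80% cardiac share gives 14 points against a half-width of 8.6. Every size here rests on assumed stratum rates and case mix, and the recruitment figures also assume that 25 + 25 is reached. If the strata behave alike, nothing is distorted. The documents do not support the stronger conclusion that the planned pooled rates are materially biased.

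**What to change.** 1. In C.8(b), report recruitment (among those approached), retention and adherence with confidence intervals separately for the cardiac and non-cardiac thoracic strata, alongside the pooled rates.
2. State the achieved mix with every pooled rate: numbers approached for recruitment, numbers enrolled for retention and adherence.
3. Give an overall rate weighted to the eligible case mix only as a secondary figure, and only if eligible patients are logged by stratum, including those never approached.
4. In C.1, and in the matching sentence of the abstract, describe the cohort as consecutive within stratum so that it agrees with C.2.

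**Cost.** No new patient procedures are needed. C.5 already records the planned operation's CPT codes for participants. The documents do not say that surgical group is kept for patients who decline or are never approached, so one screening-log field may be needed.

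The stratum intervals are wider, about ±18 points at n = 25 and 70%, and wider still if enrolment falls short. A weighted overall rate can also lose precision. With assumed rates of 90% and 70% and a 30% cardiac share, it moves from 80% to 76%. Its half-width grows from 1.96 × √(0.25 × 0.09/25 + 0.25 × 0.21/25) = 10.7 points to 1.96 × √(0.3² × 0.09/25 + 0.7² × 0.21/25) = 13.1 points. The stratum results should therefore be presented as estimates, without a test of whether the groups differ.
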